#### **Pharmacokinetics**

Pharmacokinetic variables reflecting serum OTX015/MK-8628 exposure will be evaluated in the dose escalation part of the study and in selected patients from the expansion cohort. Six blood samples will be drawn over the first 7 hours of **day 1 of cycle 1, T0** (immediately before OTX015/MK-8628 intake), **T15min** (±5 min), **T1h** (±15min), **T2h** (±15min), **T3h** (±15min) post-dose.

#### **EVALUATION CRITERIA**

## **Evaluation Populations**

Evaluable for DLT: patients who receive at least 85% of the planned dose of study drug (18 days for Regimen 1, or 6 days for Regimen 2) or experience DLT during the first 21-day cycle.

Treated population: patients who receive at least one dose of study drug.

Evaluable for efficacy: patients who receive at least 2 complete cycles (6 weeks) of treatment and have undergone baseline assessment and one on-study tumor assessment, or who discontinue early due to disease progression.

## **Endpoints**

Primary: The number of patients experiencing at least one DLT in cycle 1 (day 1 to 21) for each of the two regimens independently.

#### Secondary:

*Safety:* Incidence, severity and relationship of AEs, laboratory abnormalities, SAEs, discontinuations due to AEs, dose adaptations due to AEs, and DLT.

*Efficacy:* The number of patients with clinical benefit (defined as complete response, partial response or stable disease) and progressive disease based on the best overall response from tumor evaluations performed every 2 cycles, according to RECIST v1.1 or PCWG2, and tumor marker assessment.

*Pharmacokinetics*: Plasma parameters of OTX015/MK-8628 including  $C_{max}$ ,  $C_{min}$ ,  $T_{max}$ ,  $AUC_{[0-\infty]}$ ,  $Vd_{ss}$ ,  $t_{1/2}$ , CL.

#### Statistical Methods

The dose escalation part of the study is designed to assess the safety of OTX015/MK-8628 in this patient population. The small numbers per cohort are not intended for statistical hypotheses. Treatment decisions will be made by the SMC.

The expansion cohort part will start once the MTD and a regimen are determined. Ten patients will be enrolled per indication to give a total of 50 evaluable patients for efficacy.

Quantitative variables will be summarized using descriptive statistics. Continuous variables will be presented as N, mean and/or median, standard deviation, range. Categorical variables will be presented using frequencies and percentage.

Patient disposition and demographics will be analyzed in all included patients, response will be analyzed in patients evaluable for efficacy, and safety will be analyzed in the treated population with an additional analysis in patients evaluable for DLT for the dose escalation part.

Data will be analyzed according to dose level and regimen for the dose escalation part of the study, and according to indication and/or regimen for the dose expansion part of the study.

#### **Total Number of Patients**

Dose escalation part:

Up to 48 patients evaluable for DLT (i.e. up to 24 patients per regimen) will be accrued depending on the number of DLTs encountered. The final sample size will depend on the number of DLTs encountered at each DL, and may be increased if within the two proposed regimens and four planned DLs, MTD is not reached and additional DLs are required.

Expansion cohort part:

Once the MTD is established with at least 3 patients having received at least 2 cycles of study drug, an expansion cohort of up to 50 additional evaluable patients (10 patients per indication) will be enrolled. The regimen used in the expansion cohort will be decided for each indication by the SMC.

#### STUDY SCHEDULE

Parameter		Day 1 visit		Weekly	Day 1	Treatment
	visit	every	week	cycles	visit of	discontinuation
	(≤2 weeks	cycle	cycles 1+ 2	1+2	C3, C5,	visit (35±5 days)
	before		then		C7 etc.	after last
	treatment)		weekly			treatment intake
Informed consent	X					
Eligibility criteria	X					
Demographics, medical history	X					
Diagnosis, prior treatment for malignancy	X					
Physical examination, PS, vital signs 	$X^1$	X				X
Pregnancy test if child-bearing potential	X					
(urine test)						
Baseline symptoms and complaints	X					
Concomitant medication	X	X				X
Complete blood count (CBC) 	X	X	X			X
INR and Factor VII	X	X		X		X
Serum chemistries 	X	$X^3$		$X^3$		X
Drug dispensation						
Regimen 1		QD				
		continuous				
Regimen 2		Days 1-7				
		q3w				
Adverse events		X				X
CT, MRI, chest X-ray (PA and lateral),	$X^4$			<del>-</del>	$X^4$	X
bone scan						
Tumor markers 	X	X				X
PK blood sampling		$X^6$				
Other investigations as indicated	X	X		X		X

- 1) Vital signs include temperature, blood pressure, and pulse; Body weight at each visit and height at baseline only;
- 2) Hemoglobin, RBC counts, WBC and differential, platelet counts;
- 3) Minimum: Na, K, Ca, Mg, P, Cl, HCO3, creatinine, total protein, albumin, glucose, alkaline phosphatase, total bilirubin, AST, ALT, LDH; from cycle 3 on, in the absence of  $\geq$  grade 2 abnormalities, these tests will be performed every cycle, otherwise they are to be done weekly until resolution to baseline levels or < grade 2. All patients with specific liver test abnormalities (see DLT definition) should be monitored weekly until all abnormalities return to normal or to the baseline state. For patients with isolated total bilirubin increases >2 x ULN or 2 x baseline (if elevated at baseline), monitoring should be every 2 weeks until bilirubin returns to normal or to the baseline state;
- 4) Radiologic exams (CT, MRI, chest X-ray) performed as part of the patient's standard follow-up within 4 weeks prior to the first treatment cycle, are acceptable. Radiologic assessment will be performed every 2 cycles (6 weeks) as per RECIST 1.1 or PCWG2 until progression; Bone scans are mandatory in CRPC patients and will be performed every 4 cycles (12 weeks) until progression;
- 5) As appropriate for tumor type;
- 6) Pharmacokinetics will be performed in cycle 1 only, during the dose escalation part of the study and in selected patients from the expansion cohorts: **T0** (just before OTX015/MK-8628 intake), then **T15min** (±5 min), **T1h** (±15min), **T2h** (±15min), **T3h** (±15min) post-dose.

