# **Pharmacokinetic Findings**

PK showed dose-proportional increases in exposure ( $C_{max}$  and AUC) from 10 mg to 120 mg QD, (see Figure 2).  $T_{max}$  occurred between 1 and 4 hours (for the oral formulation used in this study  $T_{max}$  is expected between 1 to 3 hours, but limited sampling points precluded more accurate assessment of T and  $C_{max}$ ). Mean clearance was 9.9 (range, 6-12) L/h, mean volume of distribution was 68 L, and mean terminal half-life was 4.7 (range, 3.2-5.7) hours. Preliminary population PK analysis suggests that interpatient variability may be explained by lean body mass and/or body weight. These parameters appear to play a role in clearance variation, as patients with higher lean body mass display increased clearance and volume of distribution.

Trough (pre-dose) Dose N pts  $C_{max}$ AUC0-24h Cy1D1 Cy1D8 Cyl D1 (nM) (nM)  $(\mu g \cdot h/L)$ DL1 8 267 46 962 10 mg QD (121 - 424)(18 - 81)(648 - 1,349)103 2,592 DL 2 6 560 (357 - 844)(84 - 127)(1,809 - 4,223)20 mg QD DL3 8 1,274 230 4,722 40 mg QD (663 - 3,029)(53 - 897)(3,951 - 5,292)7 424 10,420 DL4 2,539 (1,085 - 4,593)(152 - 1331)(7,229 - 15,760)80 mg QD **DL4 BID** 13 1,128 638 10,540 (269 - 924)40 mg x 2 (699 - 1,810)(5,898-19,720)DL5 13 2,383 764 14,815\* (194 - 2,016)120 mg QD (1,412 - 4,055)(9,522 - 26,953)

Table 8: Mean (range) PK parameters (N=47)

The BID schedule was explored to maintain or increase trough concentrations, while not increasing  $C_{max}$ . This goal was achieved, as trough concentrations were significantly higher with the BID schedule, compared to the QD schedule, with the same daily dose, while similar exposures were obtained. Likewise, trough concentrations at DL5 (120 mg) QD achieved similar or higher trough concentration than 40 mg BID. Since both dose/schedule exceed the MTD for OHM patients, it is tempting to assume that thrombocytopenia is related to continuous high trough concentration.

[figure not shown]

Figure 2: Individual AUC0-24h versus Dose Level

\*AUC calculated on 12 patients only

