# 7.2 Evaluations During Study Treatment

#### Visit: Day 1 of each cycle

For cycle 1, patients participating in pharmacokinetics will be observed for  $\geq 8$  hours after the first study drug administration to collect PK blood samples and check vital signs, when appropriate.

- Physical examination, PS, vital signs, body weight
- CBC
- INR, Factor VII
- Serum chemistries: all patients with specific liver test abnormalities (see Section 5.2.4) should be monitored weekly until all abnormalities return to normal or to the baseline state. For patients with isolated total bilirubin increases >2 x ULN or 2 x baseline (if elevated at baseline), monitoring should be every 2 weeks until bilirubin returns to normal or to the baseline state. DILI may develop or progress even after the causative drug has been stopped.
- Concomitant medications
- Adverse events
- Tumor markers, as appropriate for tumor type; as far as possible, measures must be made in the same laboratory
- Dispensing of study drug (adequate quantity until day 1 visit of next cycle)
- Day 1 of cycle 1 only: PK blood sampling in patients included in the dose escalation part of the study and selected patients from the expansion cohort (see Section 10 for full PK details): T0 (just before OTX015/MK-8628 intake), T15min (±5 min) post-dose, T1h (±15 min) post-dose, T2h (±15min) post-dose, T3h (±15min) post-dose, and T7h (±15min) post-dose
- Day 1 of every 2nd cycle (C3, C5, C7, etc.; i.e., every 6 weeks): Tumor imaging (CT, MRI, and/or chest X-ray, as indicated) and response assessment
- Day 1 every 4th cycle (C5, C9, C13 etc.; i.e., every 3 months): Bone scan for CRPC patients

Twice a week for cycles 1 and 2 then weekly thereafter

CBC

Weekly for cycles 1 and 2

- Serum chemistries; from cycle 3 on, in the absence of  $\geq$  grade 2 abnormalities these tests will be performed every cycle; otherwise they are to be done weekly until resolution to baseline levels or  $\leq$  grade 2.
- INR, Factor VII

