#### 10 PHARMACOKINETICS ASSESSMENTS

#### 10.1 Sample collection

PK sampling will be performed in all patients enrolled in the dose escalation phase and selected patients from the expansion cohort.

A plasma sampling schedule including a total of 6 time-points over the first 7 hours of **day 1 of cycle 1** will be performed to characterize the PK profile of OTX015 ( $C_{max}$ ,  $C_{min}$ ,  $T_{max}$ , AUC  $_{[0-\infty]}$ , Vd $_{ss}$ ,  $t_{1/2}$ , and CL), as follows: **T0** (immediately before OTX015/MK-8628 intake), **T15min** ( $\pm 5$  min), **T1h** ( $\pm 15$ min), **T2h** ( $\pm 15$ min), **T7h** ( $\pm 15$ min) post-dose.

Blood samples of 3.0 mL will be collected in EDTA tubes, inverted a few times to mix the anticoagulant and then processed as soon as possible (within 15 min). Samples will be centrifuged at 1500 g (4,000 rpm for a 14-15 cm centrifuge) at +4°C for 10 minutes. Plasma will be immediately aliquoted and stored in airtight stoppered polypropylene tubes at -20°C.

In total, six blood samples of 3.0 mL each will be collected, i.e. approximately 18 mL of blood will be drawn per patient from a peripheral venous access for PK analysis.

Blood samples must be sent as soon as possible to the laboratory for analysis, to allow for availability of results at the SMC meeting. If two patients in the same center are treated at the same time or a few days apart, samples of these two patients should be sent together.

All samples will be labeled with:

- Sponsor and Protocol Number
- UPN and patient initials
- Sample number with actual date and time of collection

All samples must be shipped at -20°C to:

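### The cycle 1 day 1 PK draw times take three different forms in four places, and the schedule footnote sites are likely to work from stops at 3 h, leaving t1/2, CL and AUC(0-inf) poorly estimated

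*Protocol*

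**What the plan says.** PK is sampled on day 1 of cycle 1 in all dose-escalation patients and in selected expansion patients. The draw times appear in four places.

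- **Synopsis, Pharmacokinetics:** the text opens "Six blood samples will be drawn over the first 7 hours of" that day, but the list is T0 followed by "T15min (±5 min), T1h (±15min), T2h (±15min), T3h (±15min) post-dose". That is five draws, the last at 3 h.
- **Study Schedule, footnote 6:** the same five draws, with neither a total nor a time window.
- **Section 7.2, day 1 visit:** T0, 15 min and 1 h, then "T2h (±15min) post-dose, T3h (±15min) post-dose, and T7h (±15min) post-dose". That is six draws. The item refers the site to Section 10 for the full details.
- **Section 10.1:** it announces "A plasma sampling schedule including a total of 6 time-points over the first 7 hours of" day 1, but the list runs T0, 15 min and 1 h and ends "T2h ( $\pm 15$ min), T7h ( $\pm 15$ min) post-dose". That is five draws, with none at 3 h. The same section adds: "In total, six blood samples of 3.0 mL each will be collected, i.e. approximately 18 mL of blood will be drawn" per patient.

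Section 11.2 names Cmax, Cmin, Tmax, AUC(0-inf), Vdss, t1/2 and CL as secondary PK endpoints. Section 10.2 plans a nonlinear mixed-effects analysis. SAP Section 2.4 allows either non-compartmental or mixed-effects analysis and asks for parameters as appropriate to the method used. The SAP gives no sampling times.

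**The concern.** Footnote 6 hangs on the visit schedule and carries no count or window, so nothing tells a site using it that a draw is missing. Section 7.2 is complete, but it sends the reader to a section whose own list is short by one.

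The omitted times matter for this drug. Section 1.3.3.2 reports Tmax between 1 and 4 h (1 to 3 h expected for this formulation) and a mean half-life of 4.7 h (3.2 to 5.7). Sampling that ends at 3 h stops near the peak. A list without 3 h has nothing between 2 and 7 h to locate a peak at 3 or 4 h. The same section says of Tmax and Cmax in the earlier study that "limited sampling points precluded more accurate assessment of" them.

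PK also feeds decisions. The charter in Appendix 4 requires day 1 PK from the three patients of a cohort at the safety committee meeting, and Section 3.2 has PK weigh in the MTD decision, particularly when no DLT is seen. Cohorts are 3 to 6 patients, so one or two truncated profiles are a large share. A draw missed on day 1 cannot be recovered.

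**Working it through.** **1. Count against the stated total.** Section 10.1 states 6 samples x 3.0 mL = 18 mL.

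| Place | Draws listed | Count | Volume |
|---|---|---|---|
| Synopsis | T0, 15 min, 1, 2, 3 h | 5 | 15 mL |
| Footnote 6 | T0, 15 min, 1, 2, 3 h | 5 | 15 mL |
| Section 10.1 | T0, 15 min, 1, 2, 7 h | 5 | 15 mL |
| Section 7.2 | T0, 15 min, 1, 2, 3, 7 h | 6 | 18 mL |

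Only Section 7.2 reproduces the stated figure. The union of all four lists is that same list.

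**2. Model inputs.** Section 1.3.3.2 gives CL 9.9 L/h and V 68 L, so k = 9.9/68 = 0.1456 per h and t1/2 = ln 2 / 0.1456 = 4.76 h, against the stated 4.7 h. Seven hours is 7/4.76 = 1.5 half-lives. Assumed here: one compartment with first-order absorption, and ka solved from Tmax = ln(ka/k)/(ka - k).

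**3. Share of AUC(0-inf) observed by time T:** 1 - (ka·exp(-kT) - k·exp(-ka·T))/(ka - k). For Tmax 1 h (ka = 3.252) and T = 3 the second term of the numerator is negligible: 1 - (3.252 x 0.646)/3.106 = 0.32.

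| Tmax | ka | By 3 h | By 7 h | Post-peak draws, list ending at 3 h | Post-peak draws, Section 7.2 list |
|---|---|---|---|---|---|
| 1 h | 3.252 | 32% | 62% | 2 and 3 h | 2, 3 and 7 h |
| 2 h | 1.200 | 27% | 59% | 3 h | 3 and 7 h |
| 3 h | 0.638 | 21% | 54% | none | 7 h |
| 4 h | 0.395 | 16% | 47% | none | 7 h |

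With the 7 h draw, 38-46% is still extrapolated for Tmax 1 to 3 h (100 - 62 to 100 - 54), and 53% at 4 h.

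**4. One patient fitted alone.** T0 precedes the first dose and carries no information. With J the derivatives of log concentration with respect to log CL, log V and log ka at the remaining times, the covariance is s²·(J'J)⁻¹. Log-scale standard errors at an assumed residual error s = 20%:

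| Tmax | CL: to 3 h | CL: 10.1 list | CL: 7.2 list | t1/2: to 3 h | t1/2: 10.1 list | t1/2: 7.2 list |
|---|---|---|---|---|---|---|
| 1 h | 0.92 | 0.21 | 0.21 | 1.24 | 0.33 | 0.33 |
| 2 h | 2.35 | 0.28 | 0.27 | 3.29 | 0.59 | 0.50 |
| 3 h | 5.22 | 0.60 | 0.50 | 8.17 | 1.47 | 1.10 |

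A standard error of 0.92 is a factor of exp(0.92) = 2.5 either way; 0.21 is a factor of 1.23. The errors scale with s. At s = 10% the half-life figures to 3 h are still 0.62, 1.65 and 4.08.

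**5. Pooled analysis.** First-order population information for N = 24 (the planned maximum per regimen), with variance JΩJ' + s²I, assumed between-patient SD 0.3 to 0.5 and s 0.1 to 0.3. Relative standard error of CL:

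| Tmax | All stop at 3 h | 7.2 list |
|---|---|---|
| 1 h | 11-30% | 6-12% |
| 2 h | 25-73% | 7-13% |
| 3 h | 54-160% | 8-18% |

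**The case against.** A reader might infer that a site following the footnote collects no elimination-phase sample, so that t1/2, CL and AUC(0-inf) cannot be derived at all. The documents do not support that. With Tmax at 1 to 2 h, inside the range the protocol expects, the 3 h draw is already past the peak; only at 3 h or later is there none. Section 10.2 plans a mixed-effects analysis, which can borrow from patients who have a 7 h draw, and the SAP asks only for parameters suited to the method. If every patient stopped at 3 h and Tmax were 1 h, population CL would still have a relative error of 11-30%.

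The full list is not a cure either. At Tmax 3 h its standard error for an individual half-life is 1.10, about a three-fold error, and a large part of AUC(0-inf) remains extrapolated.

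The protocol also signals what it means. The synopsis and Section 10.1 both say six samples over 7 hours, and PK patients are observed for at least 8 h. Nothing shows that any site stopped at 3 h, so a claim that dose levels are in fact not comparable would be conjecture. The MTD is defined by DLT counts; the synopsis says only that PK may be considered, which is weaker than Section 3.2. The missing 3 h item in Section 10.1 could be a loss in PDF conversion and should be checked against the source.

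All of this stands and limits the size of the point. It does not remove the contradiction. The synopsis and footnote share the same omission, and footnote 6 offers no cue that anything is missing.

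**Conclusion.** The passages conflict and need reconciling. That rests on counting alone: three lists in four places, one of which agrees with the stated total.

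For a patient sampled only to 3 h, about 21-32% of AUC(0-inf) is observed instead of 54-62% (Tmax 1 to 3 h). Individual or non-compartmental t1/2, CL and AUC(0-inf) are then not usefully estimable. Mixed-effects estimates are possible but imprecise and dependent on the model, increasingly so as Tmax moves later. Dropping the 3 h draw, as Section 10.1 reads, costs CL little and mainly weakens the location of a peak after 2 h.

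The coverage figures depend on the one-compartment model and the earlier study's mean CL and V. The standard errors depend also on the assumed residual and between-patient variability. The direction holds throughout the ranges tried.

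**What to change.** Put the Section 7.2 list (T0, T15min, T1h, T2h, T3h, T7h) into the synopsis, Study Schedule footnote 6 and Section 10.1, with the existing windows. It is the protocol's own list and the only one that fits its count, duration and volume.

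For any patient sampled only to 3 h, flag the profile, keep the concentrations in the mixed-effects model, and do not report non-compartmental t1/2, CL or AUC(0-inf). PK is analyzed and reported separately, so this rule belongs in the PK analysis plan.

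The cost is a clarification amendment or site memo and a short addition to that plan. There is no extra blood, since six 3.0 mL samples are already budgeted, and no extra visit time, since patients stay at least 8 h. The SAP already reports the absence of response in CRPC patients and describes a BID regimen that this protocol version lacks. Sampling may therefore be largely complete, and later PK text may exist. In that case the flagging rule is the part that still has effect.

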#### ABBREVIATIONS AND DEFINITIONS

AE Adverse Event
AL Acute Leukemia

ALK Anaplastic Lymphoma Kinase ALT Alanine Aminotransferase

ALL Acute Lymphoblastic Leukemia

AML Acute Myeloid Leukemia ALP Alkaline Phosphatase

AST Aspartate Aminotransferase

AUC Area Under The Plasma Concentration Versus Time Curve

BC Breast Cancer

BET Bromodomain and Extraterminal

BID Twice Daily
BRD Bromodomain

BRDT BRD Testis-Specific Protein

CBC Complete Blood Count

CFR Code of Federal Regulations
CL Total Plasma Clearance

Cmax Peak Concentration
Cmin Residual Concentration
CNS Central Nervous System

CT-scan Computerized Tomography scan

CR Complete Response

CRPC Castrate-Resistant Prostate Cancer

DCF Data Correction Form
DILI Drug Induced Liver Injury

DL Dose Level

DLT Dose Limiting Toxicity
ECI Events of Clinical Interest
eCRF Electronic Case Report Form

EML4 Echinoderm Microtubule-Associated Protein-Like 4

ER Estrogen Receptor

FISH Fluorescence In Situ Hybridization
GnRH Gonadotropin Releasing Hormone

Hb Hemoglobin

HER2 Human Epidermal Growth Factor Receptor 2

IEC Independent Ethics Committee

ICF Informed Consent Form IHC Immunohistochemistry

INR International Normalized Ratio
IRB Institutional Review Board

KRAS Kirsten Ras

LDH Lactate Dehydrogenase

LMWH Low Molecular Weight Heparin
MRI Magnetic Resonance Imaging
MTD Maximum Tolerated Dose

NCI-CTCAE National Cancer Institute -Common Toxicity Criteria for Adverse Events

NMC NUT Midline Carcinoma

NSCLC Non-Small Cell Lung Cancer

NUT Nuclear Protein in Testis

OHM Other Hematologic Malignancies

OS Overall Survival

PCWG2 Prostate Cancer Clinical Trials Working Group

PD Progressive Disease

PFS Progression-Free Survival
PgR Progesterone Receptor
PIL Patient Information Leaflet

PK Pharmacokinetics
PR Partial Response
PS Performance Status

P-TEFb Positive Transcription Elongation Factor b

QD Once Daily RBC Red Blood Cells

RECIST Response Evaluation Criteria In Solid Tumors

SAE Serious Adverse Event

SAERF Serious Adverse Event Report Form

SAR Suspected Adverse Reaction SCC Squamous Cell Carcinoma

SD Stable Disease

SMC Safety Monitoring Committee

SUSAR Serious, Unexpected Suspected Adverse Reaction

t1/2 Terminal Half-Life

TEAE Treatment Emergent Adverse Event

Tmax Time to Peak Concentration
TNBC Triple-Negative Breast Cancer

ULN Upper Limit of Normal UPN Unique Patient Number

UPLC-MS/MS Ultra Performance Liquid Chromatography, with tandem Mass Spectrometry

Vdss Volume of Distribution At Steady State

WBC White Blood Cell

#### 1 BACKGROUND

#### 1.1 Bromodomain and Extraterminal (BET) Protein Inhibition

In cancer, pathologic activation of c-MYC plays a central role in disease pathogenesis, by the coordinated upregulation of a transcriptional program influencing cell division, metastatic adaptation and survival (Dang et al., 2009)(Kim et al., 2008). Amplification of MYC is one of the most common genetic alterations observed in cancer genomes (Beroukhim et al., 2010), and the validation of c-MYC as therapeutic target is supported by numerous lines of experimental evidence (Stewart et al., 1984)(Leder et al., 1986)(Harris et al., 1988)(Soucek et al., 2002)(Jain et al., 2002)(Fukazawa et al., 2010). Nevertheless, despite the central importance of MYC in cancer pathogenesis, conventional approaches toward its direct inhibition have not proven successful. The absence of a clear ligand-binding domain is a formidable obstacle to direct inhibition, a challenging feature shared by many compelling transcriptional targets in cancer (Darnell, 2002). Considering chromatin as a platform for signal transduction (Schreiber and Bernstein, 2002), the inhibition of MYC transcription and function has been achieved through displacement of chromatin-binding, co-activator proteins, the bromodomains (BRD), using competitive small molecules (Delmore et al., 2011).

BRDs are protein interaction modules that specifically recognize  $\varepsilon$ -N-acetylated lysine residues (Mujtaba et al., 2002)(Filippakopoulos et al., 2012). BRDs are common in nuclear proteins that regulate gene transcription and chromatin organization and play a key function of recruiting these protein complexes to acetylated chromatin. Dysfunction of BRD-containing proteins has been linked to the development of diverse diseases, and in particular to the development of cancer (Muller et al., 2011). BRDs are highly sequence diverse but share a conserved fold comprised of a left-handed bundle of four alpha helices ( $\alpha Z$ ,  $\alpha A$ ,  $\alpha B$ ,  $\alpha C$ ) (Dhalluin et al., 1999). The acetyl-lysine side chain is typically anchored by a hydrogen bond to a conserved asparagine residue and has water-mediated interactions with a conserved tyrosine (Filippakopoulos et al., 2012)(Owen et al., 2000). Crystal structures of BET complexes with di-acetylated histone 4-tail peptides showed that the first BRDs of BRD4 and BRDT may accommodate two acetyl-lysines in a single site (Filippakopoulos et al., 2012)(Morinière et al., 2009).

The BET family of BRD proteins, which includes BRD2, BRD3, BRD4, and BRD testis-specific protein (BRDT), are epigenetic reader proteins that bind acetylated lysine residues on histones playing critical roles in cellular proliferation and cell-cycle progression (Dey et al., 2009). BRD4 binds to the positive transcription elongation factor b (P-TEFb), a cyclin-dependent kinase, and stimulates RNA polymerase II-dependent elongation (Yang et al., 2005)(Jang et al., 2005). BRD4 is critical for survival of several diverse tumors due to its function promoting transcription of growth-promoting and anti-apoptotic genes (Filippakopoulos et al., 2010), which has prompted the development of potent and selective protein interaction inhibitors targeting BET BRDs.

The biological action of BET proteins occurs through a protein-protein interaction (BET protein binding to an acetylated histone protein) and, as such, this biochemical activity has historically possessed poor tractability for small molecule drug discovery identification. The identification by Chung and colleagues (Chung et al., 2011) of potent, selective BET inhibitors was not the result an oncology drug discovery effort to "drug" the BRD4 protein to target NMC, but rather was fortuitous, being the result a high-throughput screen to identify molecules for potential use in atherosclerosis (apolipoprotein A1 upregulation). In independent studies during the same time period, Mitsubishi Tanabe scientists reported the discovery and development of thienotriazolodiazepine as a BET inhibitor (including OTX015) [Mitsubishi Tanabe Pharma Corporation. Antitumor agent. WO 2009084693; 2009]. Building on these findings, Bradner and colleagues synthesized a thienotriazolodiazepine, JQ1(Filippakopoulos et al., 2010). The initial presumption of low tractability of the BET proteins has proven not to be the case, as multiple

researchers have identified other potent, selective BET inhibitors with substantially different chemical structures (Filippakopoulos et al., 2010)(Nicodeme et al., 2010)(Dawson et al., 2011)(Picaud et al., 2013). The crystal structures of these small molecule inhibitors bound to BRD4 illustrate that the binding pocket, which also binds acetyl-lysine, is small, deep, and hydrophobic.

